#### **OBJECTIVES:**

The aims of this study are to:

- Determine if fixed dose heparin infusions at a rate of 500 units/hour are sufficient to maintain a target anti-Xa of 0.1-0.35 IU/mL for VTE prophylaxis in patients undergoing microsurgical procedures.
- Develop and implement a pilot protocol to titrate heparin drips initiated at 500 units/hour following microsurgical procedures to ensure patients have sufficient VTE prophylaxis.

Hypothesis: Fixed dose heparin drips at 500 units/hour are not sufficient to maintain the target anti-Xa of 0.1-0.35 IU/mL for VTE prophylaxis in all patients undergoing microsurgical procedures.

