#### **DESIGN:**

All patients will be enrolled in the observational arm of the study. This portion will examine anti-Xa levels in response to fixed dose unfractionated heparin drips at 500 units per hour.

Patients with out of range (0.1-0.35 IU/mL) anti-Xa levels will cross over to the interventional arm of the study. These patients will receive real time unfractionated heparin dose adjustment and repeat lab draws.

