**STATISTICAL METHODS, DATA ANALYSIS AND INTERPRETATION:**

- Sample estimate
  - o An estimate of five patients per month is anticipated for the pilot study period (October 1, 2016 to March 1, 2017) for a total of 25 patients.
- Data analysis
  - o Continuous data will be analyzed using the student's t-test.
  - o Categorical data will be analyzed by the Fisher's exact test.
- Power calculation
  - o This is a pilot study whose explicit purpose is to generate preliminary data on pharmacodynamics of intravenous heparin drips at 500 units/hour, as well as the impact of a pharmacist-drive dose adjustment algorithm. By definition, pilot studies do not require power calculations as they are exploratory in nature.

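### The hypothesis is met by one out-of-range patient and sets no adequacy threshold, so confirming it says little about whether 500 units/hour is sufficient

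*Combined protocol and SAP*

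**What the plan says.** The first aim, under Objectives, is to "Determine if fixed dose heparin infusions at a rate of 500 units/hour are sufficient to maintain a target anti-Xa of 0.1-0.35 IU/mL". The hypothesis attached to it is "Fixed dose heparin drips at 500 units/hour are not sufficient to maintain the target anti-Xa of 0.1-0.35 IU/mL for VTE prophylaxis in all patients", with the population then given as those having microsurgery.

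The Design section puts every patient in an observational arm: "This portion will examine anti-Xa levels in response to fixed dose unfractionated heparin drips at 500 units per hour". It also supplies the event for each patient: "Patients with out of range (0.1-0.35 IU/mL) anti-Xa levels will cross over to the interventional arm of the study". It does not state how many levels are taken on the fixed rate or which one classifies the patient.

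The Statistical Methods section gives an accrual estimate, "for a total of 25 patients". It names the t-test for continuous data and, for the rest, says "Categorical data will be analyzed by the Fisher's exact test". It does not say what is compared, and it names no threshold, one-sample test or confidence interval. On power it says: "By definition, pilot studies do not require power calculations as they are exploratory in nature".

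**The concern.** The aim asks whether the fixed rate is sufficient. The hypothesis asks only whether it fails to be sufficient in all patients. On that reading one out-of-range patient settles the matter, and so would one mishandled or misclassified sample.

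No section says what proportion in range would be good enough, and the named tests do not fill the gap. Fisher's exact test compares proportions between groups; it does not set or estimate an acceptable proportion in a single group.

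What is at stake is how the first aim is interpreted. A rate that keeps nine patients in ten within range and a rate that keeps two in ten within range would both very probably be reported as confirming the hypothesis. That word would tell a reader little about which of the two had been found.

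The sentence is also ambiguous. It can be read as saying that the rate is insufficient in every patient, and under that reading one patient would not be enough.

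**Working it through.** **Inputs.** Sample size 25, target range and hypothesis: from the documents. True out-of-range share p: not in the documents, so a range is assumed. Patients are taken as independent and classified once each, which is also an assumption. If several levels were taken and any one out of range counted, the per-patient p would be higher.

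**The plan's own figure.** Five patients a month over the five months from 1 October 2016 to 1 March 2017: 5 × 5 = 25. This reproduces. It is an accrual estimate, so there is no power figure to check.

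**Step 1: probability that the hypothesis is met.** P(at least 1 of 25 out of range) = 1 − (1 − p)^25.

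| Assumed p | (1 − p)^25 | P(at least 1) |
|---|---|---|
| 2% | 0.603 | 0.40 |
| 5% | 0.277 | 0.72 |
| 10% | 0.072 | 0.93 |
| 20% | 0.004 | 0.996 |

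Solving 1 − (1 − p)^25 = 0.95 gives p = 1 − 0.05^(1/25) = 11.3%. Confirmation is therefore at least 95% probable only if the true share is about 11% or more.

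**Step 2: can the data refute it?** With 0 of 25 out of range, the exact two-sided 95% upper limit is 1 − 0.025^(1/25) = 13.7%. Even a clean sample leaves the hypothesis standing for the population.

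**Step 3: what the data can show.** Exact (Clopper-Pearson) 95% intervals for the share out of range:

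| Observed | Share | 95% interval |
|---|---|---|
| 1/25 | 4% | 0.1% to 20.4% |
| 5/25 | 20% | 6.8% to 40.7% |
| 10/25 | 40% | 21.1% to 61.3% |
| 20/25 | 80% | 59.3% to 93.2% |

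The first and last rows both confirm the hypothesis as worded, although their intervals are far apart.

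**Step 4: what a threshold would do.** Take an exact one-sided 5% rule, with tolerable shares chosen only for illustration.

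| Tolerable share | Patients out of range needed, of 25 | Type I error | Power |
|---|---|---|---|
| 10% | 6 | 0.033 | 0.38 at a true 20%; 0.81 at 30% |
| 20% | 9 | 0.047 | 0.32 at a true 30%; 0.73 at 40% |

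At true shares equal to those two tolerable values, the one-patient criterion is met with probability 0.93 and 0.996 (Step 1).

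**The case against.** The strongest reply is that this is a declared exploratory pilot, meant to produce preliminary pharmacodynamic data. Nowhere does the plan say it will announce a positive result on the strength of one patient or withhold the observed share. This stands in part. The exploratory label excuses the missing power calculation, and nothing prevents the investigators from reporting the proportion. But the hypothesis is the only criterion the plan offers for its first aim, and no section commits to reporting the proportion.

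A second reply is that the word all is deliberate. The section on standard of care describes one rate used whatever the patient's weight and without monitoring, so whether a single rate suits everyone is a fair question. That is so, but 25 patients cannot establish it: 0 of 25 is still compatible with a share of up to 13.7%.

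Three stronger readings are tempting, and the documents support none of them:

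- **That the pilot is almost certain to confirm its hypothesis.** This depends on an out-of-range share that the documents do not give. At 2% the probability is only 0.40.
- **That the pilot cannot show whether the rate is adequate.** All patients are observed on the fixed rate, and the resulting interval would reveal gross inadequacy.
- **That 25 of 25 in range would refute the hypothesis.** This mistakes the sample for the population.

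It is also fair to object that a formal test is debatable in an exploratory study and weak near its threshold, as Step 4 shows. For that reason it is only optional in the fix.

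**Conclusion.** The point holds as a flaw in the criterion, not in the data. On its natural reading the hypothesis is met by one patient in 25 and carries no threshold. Meeting it therefore goes little way towards deciding whether 500 units/hour is sufficient. A rate that keeps 90% of patients in range would still confirm it with probability 0.93, and a rate that keeps 80% in range with probability 0.996.

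These figures rest on assumed true shares, exactly 25 independent patients and one classification each. The existence of the flaw rests on none of them: it follows from the wording and from the absence of any stated tolerable share. The second reading, insufficiency in every patient, is a further reason to rewrite the sentence.

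**What to change.** 1. Reword the hypothesis around the proportion of patients whose anti-Xa is outside 0.1-0.35 IU/mL while on 500 units/hour. Classify each patient once, by a level defined in advance, so that levels taken after dose adjustment do not enter.
2. Make that proportion, with its exact (Clopper-Pearson) 95% interval, the main result for the first aim.
3. Have the investigators fix a tolerable share before enrolment and read the interval against it, using the number of patients actually enrolled. The choice of share is theirs; the 10% and 20% above are illustrations.
4. Optionally, add the exact one-sided rule from Step 4. If it is used, state its limited power beside it and recompute the cut-off for the final sample size, because 25 is only an accrual estimate. At 20 patients the cut-offs become 5 and 8; at 30 they become 7 and 11.

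The cost is a rewritten hypothesis, a definition of the classifying level and one agreed threshold. No patients need be added, and the change does not touch dosing. The downside is that the result may be inconclusive: at 25 patients the interval is wide, about 20 points either side near the middle of the range.

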#### **STUDY PROCEDURES:**

During the vascular or microvascular procedure, the attending surgeon will determine whether or not the patient will require a fixed dose heparin drip postoperatively. We will enroll a convenience sample of patients placed on fixed dose heparin drip by their surgeons—we will not dictate any portions of the patient's care intraoperatively, but rather will study patients already placed on a study-specific regimen by their attending surgeon. Once the order has been placed, the patient will be approached about joining the study and sign a consent form if agreeing to participate. Patients will be identified through an

alert in TheraDoc. If enrolled, the heparin drip will be managed according to the pilot protocol developed to maintain a target anti-Xa of 0.1-0.35 IU/mL until discontinued by the attending physician.

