**Standard of Care vs. Research-Related Procedures:**

Current practice at the University of Utah Hospital for selected microsurgical procedures is to initiate a heparin drip for patients determined to be high risk for microvascular thrombosis at a fixed rate of 500 units/hour, regardless of patient weight, with no monitoring by PTT or anti-xa.

Patients will be monitored using anti-xa levels and heparin infusion rates will be adjusted to maintain a target anti-xa of 0.1-0.35 units/mL.

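### The hypothesis is met by a single out-of-range patient, and neither named test estimates the share of patients the fixed rate keeps in range

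*Combined protocol and SAP*

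**What the plan says.** Under Objectives, the first aim is to "Determine if fixed dose heparin infusions at a rate of 500 units/hour are sufficient to maintain a target anti-Xa of 0.1-0.35 IU/mL". The hypothesis that follows is that fixed-rate drips "are not sufficient to maintain the target anti-Xa of 0.1-0.35 IU/mL for VTE prophylaxis in all patients undergoing microsurgical procedures". Neither statement gives a proportion, a threshold or an interval that would define sufficient.

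Under Design, every patient enters one observational arm on the fixed rate: "This portion will examine anti-Xa levels in response to fixed dose unfractionated heparin drips at 500 units per hour". Range status is then used patient by patient: "Patients with out of range (0.1-0.35 IU/mL) anti-Xa levels will cross over to the interventional arm of the study".

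Under Statistical Methods, Data Analysis and Interpretation, the analysis is two lines: "Continuous data will be analyzed using the student's t-test" and "Categorical data will be analyzed by the Fisher's exact test". No variables or groups are named. The sample of 25 comes from expected accrual, and a power calculation is waived because the study is a pilot.

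On measurement, the Standard of Care section says "Patients will be monitored using anti-xa levels" without a draw schedule, and Study Procedures has the infusion managed "until discontinued by the attending physician". The number of fixed-rate levels per patient is therefore open.

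**The concern.** A hypothesis of the form 'not in every patient' is settled by one patient. It would be true but would say little about how well the fixed rate performs, because a near-perfect result and a poor one give the same verdict.

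The analysis section does not make up for this. Fisher's exact test needs groups to compare, and the fixed-rate phase has one. A t-test, one-sample or two-sample, addresses means, and a mean can lie inside the range when no patient does.

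The range is also two-sided. A level under 0.1 and a level over 0.35 both fail to maintain it, but only the low one points to too little prophylaxis, which is the worry behind both aims. A reader who followed only the stated hypothesis and tests would not learn how many patients the fixed rate fails, in which direction, or how precisely that is known. Those facts are central to a pilot meant to supply preliminary pharmacodynamic data.

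**Working it through.** **Inputs from the documents.** Target range 0.1-0.35 IU/mL (Objectives, Design). Five patients a month from October 1, 2016 to March 1, 2017 (Statistical Methods). The plan's own figure reproduces: 5 per month × 5 months = 25.

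**Assumed inputs.** The documents give no in-range share, counts or levels, so those used below are illustrations.

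**1. What the hypothesis separates.** Exact (Clopper-Pearson) 95% intervals for x of 25 in range:

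| In range | Share | Exact 95% CI | Not in every patient | Insufficient in every patient |
|---|---|---|---|---|
| 24/25 | 96% | 79.6% to 99.9% | supported | refuted |
| 13/25 | 52% | 31.3% to 72.2% | supported | refuted |

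The intervals do not overlap, yet each reading of the hypothesis gives both results the same verdict. Wilson intervals (80.5% to 99.3% and 33.5% to 70.0%) lead to the same conclusion.

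**2. How easily it is supported.** With true in-range share p, 25 independent patients and one classification each, P(at least one out of range) = 1 − p^25:

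- p = 0.90: 1 − 0.0718 = 92.8%
- p = 0.95: 1 − 0.2774 = 72.3%
- p = 0.98: 1 − 0.6035 = 39.7%
- p = 0.99: 1 − 0.7778 = 22.2%

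These are chances of supporting a true but weak statement. They are not false-positive rates.

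**3. Why a mean does not answer Aim 1.** Take a constructed sample of 13 patients at 0.05 and 12 at 0.40 IU/mL.

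- Mean = (13 × 0.05 + 12 × 0.40)/25 = 5.45/25 = 0.218
- SD = 0.178; SE = 0.178/√25 = 0.0357
- 95% CI = 0.218 ± 2.064 × 0.0357 = 0.144 to 0.292
- One-sample t-test: p = 0.003 against 0.10 and p = 0.001 against 0.35

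The mean is significantly above the lower limit and below the upper one, and 0 of 25 patients are in range.

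**4. Why the classification rule must be stated.** If each level has an assumed 95% chance of being in range and levels are independent, a patient with k levels stays in range throughout with probability 0.95^k: 95.0%, 90.3%, 85.7% and 81.5% for k = 1, 2, 3 and 4. If levels are fully correlated, it stays at 95%. The all-levels share thus depends on how many levels are drawn, which the documents do not fix.

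**5. Precision available at 25 patients.** The widest exact interval is 40.9 percentage points (at 12 or 13 of 25; for 13, 72.2 − 31.3). Even 25/25 leaves a lower bound of 86.3%.

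**The case against.** The strongest reply is that little turns on the wording. The study is an exploratory pilot, no dose or go/no-go decision depends on the hypothesis, and nothing limits the report to yes or no. Aim 1 does not contain the word 'all'. Against a practice of one unmonitored rate for everyone, showing that it does not suit everyone is modest but relevant, and the hypothesis can fail: at a 99% true share it is supported only 22.2% of the time. Range status has to be determined for the crossover anyway, so the count and direction of misses can be reported from the recorded levels. The t-test example is artificial, and the plan never says that a t-test will judge whether the range is maintained.

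Much of this is fair. The data will exist, and the example shows only that a mean is not a proportion. But pilot status is used to waive a power calculation, and a proportion with an interval needs none. Aim 1 without 'all' still has no definition of sufficient. That the share could be reported does not settle which levels count or how patients with several levels are classified; left unstated, those choices can be made after the data are seen.

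It can also be objected that the remedy sets no threshold for sufficient, and that a first-level check does not settle when that level is drawn. Rewording Aim 1 as estimation removes the need for a threshold. The point about timing stands, so the time of the first level should be reported.

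**Conclusion.** The concern holds. On either reading, the hypothesis gives 24/25 and 13/25 in range the same verdict, and neither named test estimates the in-range share of the single fixed-rate cohort. On the natural reading the hypothesis would be supported with probability 92.8% or 72.3% even if 90% or 95% of patients were truly in range, assuming 25 independent patients classified once each. The shares and counts are illustrative; the logical point does not depend on them. The statement that no in-range proportion or interval is planned covers the sections from Objectives to Statistical Methods.

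This should be fixed but does not undermine the study: the data remain usable, and the gap is in what the plan commits to estimate.

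**What to change.** Restate the hypothesis and Aim 1 as estimation, for example: *Estimate the proportion of patients whose anti-Xa stays within 0.1-0.35 IU/mL while on the fixed 500 units/hour rate.*

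Add to the data analysis section:

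- *Each patient with at least one fixed-rate level is classified once, using only levels drawn before any rate change: below 0.1 or above 0.35 according to the first out-of-range level, and in range if every such level is within 0.1-0.35.*
- *The three proportions are reported with exact (Clopper-Pearson) 95% confidence intervals.*
- *The number of fixed-rate levels per patient, the time of the first level, and the number of patients with no fixed-rate level are reported. Classification by first level alone is given as a check.*
- *The conclusion rests on the in-range proportion and its interval.*

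Keep the t-test and Fisher's exact test for group comparisons, such as in-range versus out-of-range patients, and name the variables.

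The cost is rewording plus a few sentences. The analysis uses whatever fixed-rate levels are drawn and asks for no further patients or draws; it changes no dose or clinical rule. The downsides are that one patient no longer settles the hypothesis, that intervals at 25 patients are wide, and that the all-levels share must be read alongside the number of levels per patient.

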#### **PARTICIPANT SELECTION CRITERIA:**

Inclusion Criteria:

- Patients undergoing microsurgical procedures at the University of Utah Hospital ☐ Initiation of a heparin infusion at a rate of 500 units/hour postoperatively

Exclusion Criteria:

- Age <18 years old
- Pregnant
- Incarcerated

#### **DESIGN:**

All patients will be enrolled in the observational arm of the study. This portion will examine anti-Xa levels in response to fixed dose unfractionated heparin drips at 500 units per hour.

Patients with out of range (0.1-0.35 IU/mL) anti-Xa levels will cross over to the interventional arm of the study. These patients will receive real time unfractionated heparin dose adjustment and repeat lab draws.

#### **STUDY PROCEDURES:**

During the vascular or microvascular procedure, the attending surgeon will determine whether or not the patient will require a fixed dose heparin drip postoperatively. We will enroll a convenience sample of patients placed on fixed dose heparin drip by their surgeons—we will not dictate any portions of the patient's care intraoperatively, but rather will study patients already placed on a study-specific regimen by their attending surgeon. Once the order has been placed, the patient will be approached about joining the study and sign a consent form if agreeing to participate. Patients will be identified through an

alert in TheraDoc. If enrolled, the heparin drip will be managed according to the pilot protocol developed to maintain a target anti-Xa of 0.1-0.35 IU/mL until discontinued by the attending physician.

**Standard of Care vs. Research-Related Procedures:**

Current practice at the University of Utah Hospital for selected microsurgical procedures is to initiate a heparin drip for patients determined to be high risk for microvascular thrombosis at a fixed rate of 500 units/hour, regardless of patient weight, with no monitoring by PTT or anti-xa.

Patients will be monitored using anti-xa levels and heparin infusion rates will be adjusted to maintain a target anti-xa of 0.1-0.35 units/mL.

**STATISTICAL METHODS, DATA ANALYSIS AND INTERPRETATION:**

- Sample estimate
  - o An estimate of five patients per month is anticipated for the pilot study period (October 1, 2016 to March 1, 2017) for a total of 25 patients.
- Data analysis
  - o Continuous data will be analyzed using the student's t-test.
  - o Categorical data will be analyzed by the Fisher's exact test.
- Power calculation
  - o This is a pilot study whose explicit purpose is to generate preliminary data on pharmacodynamics of intravenous heparin drips at 500 units/hour, as well as the impact of a pharmacist-drive dose adjustment algorithm. By definition, pilot studies do not require power calculations as they are exploratory in nature.
